8.3 Management of Side Effects of Azithro [79]

Hypersensitivity reactions

Allergic reactions such as angioedema, anaphylaxis, Stevens-Johnson syndrome, toxic epidermal necrolysis, and DRESS have been reported rarely with azithromycin

administration. Azithromycin should be discontinued immediately in the event of a hypersensitivity reaction.

Cardiovascular events and altered cardiac conduction

Macrolides have been associated with rare QT prolongation and ventricular arrhythmias but not Azithro in clinical studies (see Rationale above). Some studies, but not all, have described an association between azithromycin and cardiovascular events and mortality [41]. Therefore, to be conservative, Azithro should be discontinued immediately in the event of a cardiovascular event and additional evaluation and management pursued as appropriate for the clinical condition, as determined by the site investigator.

GI symptoms including diarrhea, nausea, and vomiting occur frequently (>10%) in azithromycin recipients. Azithro may be administered with food to reduce GI side effects. GI side effects do not require treatment discontinuation and participants may be referred to their health care provider for symptomatic treatment (e.g., antiemetics). However, in the event of any treatment-related toxicity (GI or other), the site investigator has the option to discontinue study treatment if the side effect is intolerable or at their discretion.

Dose modification of Azithro will not be allowed in the study. If Azithro/Placebo is discontinued for toxicity reasons, all study medications should be discontinued and not be restarted.

NOTE: Grades 1 and 2 AEs associated with Azithro require no change in study treatment.

8.4 Pregnancy

The study products may be given in pregnancy. To maximize study staff safety, the proposed study will be primarily remote visit based, thus we will not get weights, ultrasounds, vitals, physical exams, etc. during study treatment. However, pregnancy information and outcomes will be captured on an eCRF, including: gestational age during study treatment, and pregnancy outcomes.

8.5 Breastfeeding

The study products may be given to women who are breastfeeding.

9.0 CRITERIA FOR DISCONTINUATION

9.1 Permanent and Premature Treatment Discontinuation

- Drug-related toxicity (see [section 8.0 Clinical Management Issues](#)).
- Participant experiencing an SAE that is considered at least possibly related to study drug.
- Requirement for prohibited concomitant medications (see [section 5.4](#)).
- Request by participant to terminate treatment.

NOTE: The reason for treatment discontinuation should be documented (e.g., concern for AE, lack of efficacy, or other reason).

- Clinical reasons believed life threatening by the physician, even if not addressed in the [toxicity section](#) of the protocol.
- **Day 0 CrCl <45 mL/min, for participants in optional intensive sampling study (see [section 6.2.4](#)).**

9.2 Premature Study Discontinuation

- Failure to take the first (directly observed/confirmed) dose of study treatment at the study entry visit.
- Request by the participant to withdraw consent.
- Request of the health care provider if she or he thinks the study is no longer in the best interest of the participant.
- At the discretion of the IRB/EC, FDA, NIAID, Office for Human Research Protections (OHRP), other government agencies as part of their duties, investigator, or industry supporter.

In the event that a participant prematurely discontinues from the study, unless they have withdrawn consent, sites will attempt to obtain information regarding vital status (including date last seen alive, hospitalization, date of death, and primary cause of death) from other sources (such as family members, other designated contacts, or clinic records) per [section 6.2.4](#).

10.0 STATISTICAL CONSIDERATIONS

10.1 General Design Issues

This is a double-blind placebo-controlled randomized trial, designed to compare the efficacy of HCQ and Azithro for the treatment of COVID-19 in adults compared to adults receiving placebo to decrease hospitalization and death during SARS-CoV-2 infection.

10.2 Outcome Measures

Primary and secondary outcome measures listed below will be addressed in the study's primary Statistical Analysis Plan, which will define the content of the Primary Analysis Report. This report will form the basis for the primary study manuscript and results reporting to ClinicalTrials.gov.

10.2.1 Primary Outcome Measure

Death from any cause or hospitalization during the 21-day period from and including the day of the first (confirmed) dose of study treatment. Hospitalization is defined as requiring at least 24 hours of acute care in a hospital or similar acute care facility, including Emergency Rooms or temporary facilities instituted

to address needs during the COVID-19 pandemic. Evaluation at a hospital or similar facility with less than 24 hours of acute care is not considered a hospitalization.

10.2.2 Secondary Outcome Measures

- 10.2.2.1 Death from any cause during the 21-day period from and including the day of the first (confirmed) dose of study treatment.
- 10.2.2.2 Death from any cause or hospitalization or urgent visit to an emergency room or clinic during the 21-day period from and including the day of the first (confirmed) dose of study treatment.
- 10.2.2.3 Death from any cause or hospitalization during the 24-week period from and including the day of the first (confirmed) dose of study treatment. Hospitalization is defined as requiring at least 24 hours of acute care in a hospital or similar acute care facility, including Emergency Rooms or temporary facilities instituted to address needs during the COVID-19 pandemic. Evaluation at a hospital or similar facility with less than 24 hours of acute care is not considered a hospitalization.
- 10.2.2.4 Premature discontinuation of study treatment due to an adverse event.
- 10.2.2.5 Occurrence of any cardiac adverse events from start of study treatment through Day 20.
- 10.2.2.6 Duration of fever defined as the last day in the participant's daily diary card on which a temperature greater than 100.4°F was recorded or a potentially antipyretic drug, such as acetaminophen or ibuprofen, was taken.
- 10.2.2.7 Duration of symptoms associated with COVID-19 disease defined as the last day in the participant's daily diary card on which a moderate or worse symptom was recorded. The set of targeted symptoms are the same ones that are used in many influenza studies, with the addition of the symptoms of loss of smell and loss of taste, which have been associated with COVID-19 infection. The symptoms from influenza studies are: cough, shortness of breath, feeling feverish, fatigue, muscle aches, diarrhea, vomiting, nausea, headache, sore throat, nasal obstruction (stuffy nose), and nasal discharge (runny nose). These symptoms are listed individually on the Study Diary that each participant will complete each day. The scoring is that used in influenza studies, whereby participants grade each symptom as absent (score 0), mild (1), moderate (2), or severe (3).
- 10.2.2.8 **Participant-specific area under the curve (AUC) of the symptom**

score associated with COVID-19 disease **over time (through Day 20)** defined as the sum of scores for the targeted symptoms (defined above) in the participant's daily diary record (each individual symptom is scored from 0 to 3).

- 10.2.2.9 Time to self-reported return to usual (pre-COVID) health.
- 10.2.2.10 Level (detectable versus not detectable, and continuous) of SARS-CoV-2 RNA from self-collected nasal and site-collected NP swabs at entry and Days 6 and 20 among subset.

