HCQ and Azithro have each been used widely for many years, for the independent indications described previously. Potential risks are described further in this section below.

HCQ

Common side effects of HCQ include headache, emesis, diarrhea, vision changes, and muscle weakness. Severe side effects are mainly limited to allergic reactions and eye toxicity, "chloroquine retinopathy" [30], and cardiac toxicity. "Chloroquine retinopathy" is a relatively serious toxicity associated with HCQ use among people taking HCQ for greater than 5 years [31]. Further, rapid-onset retinopathy has been reported in persons being treated with erlotinib and high-dose HCQ (1000 mg daily) for non-small cell lung cancer [32]. Generally, people taking **400** mg of HCQ or less per day or for short periods have a negligible risk of retinopathy, as macular toxicity is related to total cumulative dose [22]. The dose and durations proposed in this trial are unlikely to cause retinopathy [31].

HCQ can prolong the QT interval, and ventricular arrhythmias and TdP have been reported, but usually after prolonged administration [33], particularly in patients with lupus and other comorbidities such as end-stage renal disease [34-37]. **In general**, drug-induced TdP and life-threatening ventricular arrhythmias from HCQ are very rare and typically only observed when doses of 5 g or more are taken [14, 33, 38]. HCQ is a derivative of chloroquine, and the relationship between chloroquine and QT prolongation has been better defined. It is the same molecule that is associated with a prolonged QTc

interval. When chloroquine was administered to healthy adults (regimen 600 mg + 600 mg + 300 mg on Days 1, 2, and 3, respectively) the average increase in QTc interval was 28 ms (18-38 ms; 95% CI) with no cardiac AEs reported [39]. While chloroquine and HCQ are different compounds, animal toxicity studies indicate HCQ is two to three times less toxic across different species [40].

Further, the WHO states, “[d]rug-induced TdP and life-threatening ventricular tachyarrhythmias are very rare events, and there are no simple screening tests to identify people at risk.” Also from WHO, “[d]espite hundreds of millions of doses administered in the treatment of malaria, there have been no reports of sudden unexplained death associated with quinine, chloroquine or amodiaquine, although each drug causes QT/QTc interval prolongation” [38].

Azithro

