6.3.5 Medication History

A medication history must be present, including start and stop dates. The table below lists the medications that must be included in the history at screening **and updated at entry**.

Table 6.3.5-1: Medication History

Medication Category	Complete History or Timeframe
All prescription drugs	Last 7 days
Prescription drugs for high blood pressure	Last 3 months
Prescription drugs for diabetes and pre-diabetes	Last 3 months

Medication Category	Complete History or Timeframe
Prescription drugs for lung disease	Last 3 months
Prescription drugs for heart disease	Last 3 months
Prescription drugs for autoimmune disease	Last 3 months
Cancer chemotherapy	Complete history
Antiretroviral therapy	Last 3 months
Immune-based therapy	Last 3 months
Blinded study treatment	Last 12 months
CoV-related vaccines	Complete history
Alternative therapies	Last 3 months
Dietary supplements	Last 3 months

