6.3.6 Clinical Assessments

No physical exams will be conducted.

Site clinical investigators will perform a clinical assessment at enrollment **for all participants**. In their clinical judgment, they may identify some participants who are ill enough to warrant further clinical evaluation, which may result in hospitalization. They will then refer these participants for such evaluation. These participants will not start study treatment, and not be included in the analyses. While clinical judgement may not be standard across sites, the process should balance site variation.

Post entry, see [section 8.4](#) for collection requirements for pregnancy.

Refer to [section 7.2](#) for AE collection requirements.

Concomitant Medications

Post-entry, the following new and discontinued concomitant medications must be recorded:

- High blood pressure medications
- Steroids or other immunosuppressive or immunomodulatory medication
- Non-steroidal anti-inflammatory drugs (NSAIDs)
- Chemotherapy
- Antibiotics, antifungals and antivirals (including antiretrovirals)
- HCQ or chloroquine or any agent felt to have potential COVID-19 activity
- Inhalers
- Agents with QTc prolongation potential and antiarrhythmics listed in [section 5.4.1](#).

Study Treatment (Intervention) Modifications

Record any modification to treatment, treatment interruption, and permanent discontinuation of treatment, and the reason for the modification, interruption, or discontinuation.

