6.3.10 Study Diary

Distribution of Study Diary

Participants will be provided a Study Diary at study entry. The Study Diary is posted on the DMC Portal in the Forms Management Utility.

Participants will be asked to keep a log of symptoms, temperature (if possible), medications they are taking, and major events such as urgent visit to an emergency room or clinic and hospitalization in their Study Diary on Days 0-20. At study entry, participants will complete the Study Diary prior to study treatment initiation. Depending on timing of each participant's dosing, some may complete HCQ/Placebo study treatment on Day 7 instead of Day 6 and need to report a Day 7 dose. Participants will be asked to complete the diary each evening.

Review of Study Diary

The Study Diary will be reviewed by study staff with each participant at the remote and in-person visits described in the [SOE](#) and the participant's answers recorded in the Participant Study Diary eCRF. If feasible, prior to or during the remote study visits, sites will request that the participant send images of each of their study diary entries to be reviewed at the next study contact.

Participants who report worsening illness from any cause during the trial may be referred to their health care provider or closest emergency room. Such instances will be recorded at the time of the notification, and during follow-up to assess study endpoints, i.e., hospitalization or death.

Review of Treatment Adherence

The treatment adherence portion of the Study Diary will be reviewed by study staff with each participant at the remote and in-person visits (if applicable), as described in the [SOE](#). The participant's answers of timing of doses taken will be recorded in the Adherence Assessment eCRF. If any doses are missed, the reason for the missed dose will be recorded.

Collection of Study Diary

The Study Diary will be collected per the [SOE](#). **If Day 20 is conducted remotely, arrangements should be made for future transfer of study diary from the participant to the study staff (i.e., mailing the study diary or sending images).**

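### The fever-duration outcome (10.2.2.6) counts any antipyretic day whatever the reason, so regular users and late analgesic doses are scored as fever

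*Protocol*

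**What the plan says.** Protocol 10.2.2.6 reads: "Duration of fever defined as the last day in the participant's daily diary card on which a temperature greater than 100.4°F" and continues "was recorded or a potentially antipyretic drug, such as acetaminophen or ibuprofen, was taken". Either condition is enough, the drug list is open-ended, and the latest qualifying day sets the value.

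Other sections that bear on this rule:

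- **Diary (6.3.10):** "Participants will be asked to keep a log of symptoms, temperature (if possible), medications they are taking". Temperature is therefore optional. No section describes a field for the reason a drug was taken.
- **Medication history (6.3.5):** the first line of the table is "All prescription drugs", and most other lines are prescription classes. No line names over-the-counter analgesics.
- **Post-entry concomitant medications (6.3.6):** only new and discontinued drugs in listed classes are recorded. NSAIDs are on the list and acetaminophen is not.
- **Eligibility and prohibited drugs (4.2, 5.4.1):** aspirin, NSAIDs and acetaminophen are neither excluded nor prohibited.
- **Diary symptoms (10.2.2.7):** the targeted list includes "cough, shortness of breath, feeling feverish, fatigue, muscle aches, diarrhea, vomiting, nausea, headache, sore throat", so headache and muscle aches are scored separately from fever.
- **Side effects (2.1):** "Common side effects of HCQ include headache, emesis, diarrhea, vision changes, and muscle weakness".
- **Use of the outcome (10.6.2, 10.5):** fever duration is compared between arms with a two-sided stratified Wilcoxon test at 5%, and the DSMB sees it by arm at each interim review.

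**The concern.** Taking the drug is sufficient, and the last such day decides the value. Two kinds of misscoring follow.

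1. **Regular use.** Someone who takes an NSAID, aspirin or acetaminophen every day for another reason is recorded as febrile to Day 20 even if never febrile. The trial aims for at least 50% high-risk participants (10.3), a stratum that includes age 60 or older, hypertension and diabetes, so some regular users are to be expected.
2. **Occasional late use.** A participant whose fever ended on Day 3 and who takes one ibuprofen for a headache on Day 18 is scored 18 days instead of 3.

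The first kind lengthens both arms and hides part of any true difference. The second can differ by arm, because the protocol names headache as a common effect of one of the two active drugs. A rank test removes neither error, since the misscored participants keep their wrong ranks. At stake are the interpretation of one secondary outcome under objective 1.3.3 and one of the summaries shown to the DSMB.

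**Working it through.** The protocol gives no rate, spread, effect or power for fever duration, so it has no figure to reproduce. The calculation below is an illustration, and every fever and drug-use input in it is an assumption.

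**Inputs**

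- From the protocol: about 1000 per arm and a 5% loss allowance (10.4), so 1000 × 0.95 = 950 per arm; two-sided Wilcoxon at 5% (10.6.2); diary Days 0–20 (6.3.10).
- Assumed: true last fever day geometric from 0, mean 4 days on placebo and 3.4 on active (15% shorter), capped at 20.
- Simplified: strata are ignored, as is the ranking of hospitalized or deceased participants as worse.

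**Step 1. Effect of daily users on the mean**

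The capped means are 4 × (1 − (4/5)^20) = 3.95 and 3.4 × (1 − (3.4/4.4)^20) = 3.38, a difference of 0.57 days. If a share q of both arms takes a drug daily, the recorded mean is (1 − q) × true mean + q × 20, and the difference shrinks to (1 − q) × 0.57.

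| q (assumed) | Recorded placebo mean | Recorded difference |
|---|---|---|
| 0 | 3.95 | 0.57 |
| 5% | 0.95 × 3.95 + 1 = 4.75 | 0.54 |
| 10% | 0.90 × 3.95 + 2 = 5.56 | 0.51 |
| 20% | 0.80 × 3.95 + 4 = 7.16 | 0.46 |

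**Step 2. Effect of daily users on the test (simulation)**

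- With a true effect, power is about 79% with no daily users, and about 71%, 61%, 43% and 28% at 5%, 10%, 20% and 30%.
- With no true effect, rejection stays at about 5–6%, so type I error is not inflated.
- The absolute power depends on the assumed distribution. Starting the geometric at Day 1 gives 94%, 82%, 62% and 43% at 0%, 10%, 20% and 30%. The decline appears under both.

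**Step 3. Extra analgesic use in the active arm only, no true fever effect**

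Here 20% of both arms have one sporadic last use, uniform over Days 0–20. The active arm has a further 5 or 10 percentage points, with last use in the window shown. The result is the share of trials that find significantly longer fever on active (nominal 2.5%).

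| Window for the excess | 5-point excess | 10-point excess |
|---|---|---|
| Days 0–6 | about 5–6% | about 10–11% |
| Days 4–9 | about 16% | about 41% |
| Days 0–20 | about 25% | about 73% |

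The assumed background matters too. With side-effect use in Days 0–7 and no background sporadic use, the shares are about 9% and 24%. Dosing ends on Day 6 or 7 (5.1, 6.3.10), which favours the early windows. The terminal half-life of hydroxychloroquine is given as 40 to 50 days (2.1), so some later effect cannot be ruled out.

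**The case against.** **The drug condition is deliberate.** Without it, a participant whose fever is suppressed by acetaminophen would be scored as recovered, and a participant who records no temperature could not be scored at all. This stands. The flaw is the missing condition on reason and prior use, not the condition itself.

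**Regular use cannot bias a randomized comparison.** This also stands: the cost is lost power and inflated durations. A reader might infer that daily users produce false positives, but the null runs show that they do not.

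**The high-risk argument has limits.** A history of ischemic or structural heart disease is excluded (4.2.6), which removes some daily aspirin users. Aspirin is not named in 10.2.2.6 and enters only through the open-ended wording. No prevalence of regular use is given.

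**The arm bias may be small.** A reader might take the 25% and 73% figures as the expected error. The documents do not support that, because those figures place the excess use evenly over three weeks when dosing lasts about one. No headache rate is given.

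**The consequence is limited.** This is one of ten secondary outcomes. Symptom duration, symptom score AUC and return to usual health also address objective 1.3.3 and do not use the drug condition. The efficacy stopping guideline rests on the primary outcome, and fever duration is only one of several DSMB summaries. All of this stands.

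**The SAP, not shown here, could narrow the rule.** It could do so only with data that are collected. The protocol describes no recording of reason for use and no entry question on over-the-counter analgesics. The diary form itself is not in the document, so it may hold more than 6.3.10 describes.

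**Conclusion.** The point holds as a limited defect in the definition of one secondary outcome. As written, the rule scores an afebrile daily user of a potentially antipyretic drug as febrile to Day 20, and lets one late dose for another complaint override earlier fever-free days. No other section narrows it.

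The firmer consequence is dilution: power falls from about 79% to about 71%, 61% and 43% at 5%, 10% and 20% daily users. Those shares and the fever distribution are assumptions. Bias against the active arm through hydroxychloroquine headache is plausible but of unknown size. With a 5- to 10-point excess in use, a false finding of longer fever occurs in about 5–10% of trials if the excess falls in Days 0–6, and more often if it falls later or background use is lower, against a nominal 2.5%.

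The documents do not support reading this as a threat to the primary result or as a reason to drop the antipyretic condition.

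**What to change.** Keep the antipyretic condition in 10.2.2.6, but count a drug day only if both of these hold:

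- the drug was taken for fever or feverishness, recorded by one tick-box in the diary medication log;
- it is not a drug the participant took regularly before COVID-19 onset, recorded by one entry question that covers over-the-counter aspirin, NSAIDs and acetaminophen.

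Report the current definition and a temperature-only version as sensitivity analyses.

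If the diary cannot be changed, exclude only drugs used regularly before onset. Do not instead require antipyretic days to run unbroken from a documented fever. That would give zero duration to participants with no recorded temperature, which 6.3.10 allows, and to those whose fever was masked from Day 0.

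The cost is one tick-box, one question and a revised sentence. The downside is some reliance on the participant's stated reason, which the sensitivity analyses make visible. The reason has to be collected prospectively, because it cannot be reliably recovered later.
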